# **Gender and Minority Inclusion of Subjects**

Gender and minority inclusion for this project will be promoted in several ways. Enrollment will primarily be through the NYU MS Comprehensive Care Center, with a diverse patient The Health Initiative for Underserved Communities and members of its Community Health Advisory Board will be informed of the project and asked to make their members aware of eligibility.

# **Vulnerable Subjects**

Participants with MS may be considered as vulnerable subjects due to cognitive impairment; however, those who lack capacity to consent will not be enrolled in this study. For all participants, we will confirm capacity to consent with their care provided at the visit. We will also screen those with estimated overall cognitive impairment and reading ability by administering a reading measure Wide Range Achievement Test 4 (WRAT-4). It will be clearly explained and written for all potential participants that the study is entirely optional and there will be no negative consequences to their decision not to participate.

# VIII. STUDY LOCATION

Participants screening, baseline and study end visits will be completed at the NYU MS Langone MS Comprehensive Care Center, [name], or the satellite location for the

MS Center, NYU Langone Huntington Medical Center, [name]. For participants with limited mobility, visits can be completed from the participant's home.

# IX. DATA ANALYSES AND DATA MONITORING

#### **Database and Patient Information**

Data will be entered in the HIPAA- compliant NYU REDCap database designed specifically for this study. An anonymous database number will be assigned to each participant and will be used for both the Data Entry Sheet and the Patient Follow-up Sheets. The original front sheet, which includes the patient name and ID number, will be stored separately in a locked filing cabinet in a locked office. Access to this data will be restricted to study personnel only. Research data will be entered online through the secure NYU database software REDCap and source documents will be kept in a locked filing cabinet in a locked office. Patient clinical data will be entered directly into the Patient Registry (on-line entry). Participant data will be coded by the assigned ID and identifying information will not be presented or published to maintain participant privacy and confidentiality.

#### Additional Quality Assurance Measures

- Development of standard protocols to perform all data collection and follow-up activities.
- Use of standardized forms.
- Uniform criteria for patient recruitment.
- Standardized data processing.
- Regular communications between study staff and study investigators to resolve questions.
- Performance monitoring of data collection and data processing activities, as well as preparation of periodic reports and analyses on performance monitoring.
- Monthly monitoring of recruitment statistics.

#### Monitoring

We will utilize operating procedures for reviewing patient safety data and source data generated from this study. This will include weekly meetings between the PI. Co-investigators, and study coordinator. At these meetings, the entire research team will review the clinical ratings, assessments, clinical course, and medical records for each subject. Consideration of dropping any patient from the study for any reason will be discussed. If after the completion of the first 10 subjects the compliance is significantly less in one or more arm of the study relative to our previously observed compliance rates, the study will be put on hold and reviewed. Based on the extensive body of literature using tDCS across a range of conditions, and our initial participants studied to date (completed at Stony Brook Medicine, we have had >94% compliance in the active condition. Therefore, this discrepancy in compliance is not expected. We would define discrepancy in compliance as >50% difference in mean number of visits completed and/or 50% difference in number of "completers" in each condition (defined by completing at least 50% of n=5/10 sessions). If there is significantly poor compliance in the active session, we will be able to identify reasons including tolerability as well as symptom experiences. Tolerability is measured before, during and after each session and all participants will be monitored for all sessions. Safety is carefully addressed in our protocol with a series of stop criteria and clearly defined action items.

Specific attention will be given to data quality and timeliness, HIPAA-complaint, safe storage of data, and data backup of electronic source data. Attention will also be given to participant recruitment, accrual and retention, participant risk versus benefit, adverse events, and other factors that can affect study outcome, including scientific or therapeutic developments that may have an impact on the safety of the participants or the ethics of the study.

An adverse event is defined as any rating (at any time) of pain of greater than "moderate" or side effects or sensations that arise preceding, during, or following stimulation. Pain and tolerability are measured before, during and after each session. As noted, there is an extensive body of literature demonstrating the safety and tolerability of tDCS both in MS and in a range of clinical disorders. Our lab at Stony Brook Medicine administered >200 active tDCS sessions to MS participants with no pain ratings of severe or greater and no discontinued session (for any reason, safety or tolerability). Figure 3 below demonstrates these results.

Figure 3. Self-applied tDCS sessions across n=20 participants

We will submit study data safety monitoring reports to the IRB after 10 participants are enrolled in the active condition, and follow with reports for each further increment of 10 active enrollees.

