# V. DESCRIPTION OF THE PROTOCOL

# The goal of this pilot study is to establish a structured protocol for safe remotely-supervised delivery of 40 consecutive tDCS sessions (active and control conditions) to be used in a randomized, controlled double-blind clinical studies in participants with MS.

*a)* Study Design: Participants will complete a total of 40 sessions across eight weeks: training at baseline with a study technician and then monitoring (through secure online video) by the study technician for the remaining thirty-nine sessions. We will use the most common montage of bilateral dorsolateral prefrontal cortex (DLFPC) placement, with the anodal electrode placed on the left side. This offers ease of reliable electrode placement and wide therapeutic applications. Dose will be up to the target of 2.5 mA with reduction to 2.0, 1.5, or 1.0 mA based on tolerability testing at baseline. At study end, participants in the sham condition will be offered 10 open label active sessions.

**b)** Study Equipment: For the remotely-supervised sessions, participants will be given the speciallydesigned tDCS device and headset, study laptop computer for secure video monitoring with study technician (must have internet access), a detailed reference manual, and a training video. The Soterix mini-CT is uniquely designed for remotely-supervised delivery and requires a one-time use code provided by the study technician to unlock the device for one stimulation session. The device will not operate without correct headset placement and has a single-button option to abort the session. The device will also automatically abort the session if optimal conditions are not maintained. It reports and records a completion code for each session.

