# VI. METHODS AND PROCEDURES

All remotely-supervised sessions will be completed while connected to a video session with the study technician. The protocol is designed to have a decision-tree series of checkpoints that must be met in order to proceed at each step (Figure 2). These checkpoints address compliance (attendance, ability to complete the procedures as instructed, following the study guidelines) and tolerability (at any time, if any predefined events are reported). Following state of the art in tDCS research, devices will be programmed in advance by the PI to provide either active or sham sessions following current standards for blinding. During a sham session, the device is programmed to ramp up to the desired intensity (target 2.5 mA) and ramp down for the initial 60 seconds, with no current delivery during the following 18 minutes of the session, and then current is ramped up and down for 60 seconds at the end of the session. These brief periods of stimulation serve to mimic the effects of a true stimulation session. Both participants and study coordinator (who administers study outcome measures) will be blinded, and will be asked to guess the assigned condition at study end.

The PI will not be blinded to study condition. The PI or an un-blinded study technician will preprogram devices according to randomization and then provide to the study coordinator for each participant. That is, the study coordinator and participant will be blinded to which condition programmed to the assigned device. All procedures will be the same for all three conditions. Adverse events will be addressed in either condition, and the study PI will always know the assigned condition for each participant.

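### The blinded outcome rater sits in weekly per-subject review meetings with the unblinded PI, and the plan says nothing about protecting the rater's blind there

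*Combined protocol and SAP*

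**What the plan says.** Section VI (Methods and Procedures) sets the blinding roles. For the rater: "Both participants and study coordinator (who administers study outcome measures) will be blinded". What the rater must not know is also given: "the study coordinator and participant will be blinded to which condition programmed to the assigned device". For the PI: "The PI will not be blinded to study condition", and "the study PI will always know the assigned condition for each participant".

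Section IX, under Monitoring, describes how patient safety and source data are reviewed. On attendance: "This will include weekly meetings between the PI. Co-investigators, and study coordinator". On content: "At these meetings, the entire research team will review the clinical ratings, assessments, clinical course, and medical records for each subject". The same subsection describes the information collected around each session: "Tolerability is measured before, during and after each session and all participants will be monitored for all sessions".

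Section V gives the length of treatment: "Participants will complete a total of 40 sessions across eight weeks". Table 2 schedules outcome tests at mid-study, between sessions 20 and 21, and again at study end. Under Study End Visit, the final visit falls within three days of the last session.

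**The concern.** The double blind protects the Aim 2 comparison of change scores only if the person giving the tests does not know the arm. Section VI recognises this by blinding the coordinator. The Monitoring subsection then makes the same person a named attendee at a recurring, subject-by-subject review in which another participant knows every allocation. The two sections are not reconciled.

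If the rater comes to know or guess the arm, encouragement, prompting or scoring can drift in favour of active stimulation on tests that depend on an examiner. The result would be an apparent difference between active and sham that stimulation did not cause. Sections V and IX say that the Aim 2 results will be used to set sample sizes for a later, adequately powered trial, so a distorted estimate would carry forward.

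**Working it through.** No figure in the plan bears on this point, so the check is mainly a comparison of sections plus one count.

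**1. Same person, same meeting.** Section VI: the coordinator gives the outcome measures and is blinded; the PI is not. Section IX, Monitoring: the PI, the co-investigators and the coordinator meet weekly, and the whole team reviews each participant individually. Nothing limits the coordinator to part of the agenda.

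**2. Could the reviewed information point to the arm?** Three parts of the protocol suggest that it could.
- Section VI: sham delivers current only in the first and last 60 seconds, with none for the 18 minutes between.
- Section X, Risk to Participants: the adverse events that set active tDCS apart from sham are given as tingling, itching and redness.
- Section IX, Monitoring: side effects and sensations around stimulation count as adverse events, and tolerability and pain are recorded before, during and after every session.

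The plan also intends to test whether side effects differ between conditions (Sections V and IX, Aim 1 analyses), so it treats such a difference as possible.

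**3. Number of meetings before testing.**
- Sessions per week: 40 / 8 = 5.
- Weeks to mid-study (after session 20): 20 / 5 = 4, so about 4 weekly meetings.
- Weeks to study end (after session 40): 40 / 5 = 8, so about 8 weekly meetings.

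**4. Safeguards.** I looked for a closed session, masked summaries, a separate rater who does not attend, or a rule on what the PI may say. None is given. Two provisions come near. Section VI has the coordinator guess the condition at study end, which may detect a lost blind but only after the scores are in. Additional Quality Assurance Measures calls for standard procedures and forms, which narrows discretion in testing but does not keep the arm from the rater.

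**5. Which outcomes are exposed?**
- *Aim 1 completion.* The outcome is the number of participants finishing at least 32 of 40 sessions. The device records a completion code for each session, so an examiner's expectation does not enter.
- *Fatigue in Aim 2.* This rests largely on inventories that participants complete themselves, so it is less exposed.
- *Cognitive and motor tests in Aim 2.* Table 2 lists the SDMT, verbal learning, word association, pegboard and grip strength. It does not give the mode of administration; I take these to be given by an examiner. All but the SDMT are marked as optional. The SDMT is due at both mid-study and study end.
- *Which comparisons.* Two of the three arms receive active tDCS. Side-effect information could help to separate sham from active stimulation, but not the two active arms from each other.

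**The case against.** The strongest reply is that the exposure is inferred. The Monitoring text names broad classes of information; it does not say that session-level sensation or pain ratings are tabled. The instruction that the coordinator stays blinded remains in force at the meeting. This stands, and it limits the wording: the rater may be exposed. A reader might infer that allocation is announced or discussed at the meetings, but no section says so.

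A reader might also argue that seeing earlier scores at the meeting biases the comparison. That does not follow. The coordinator gives the tests and may know the earlier scores anyway. Knowing them without knowing or guessing the arm is not in itself arm-related, so this path should not be part of the point.

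A third reply is that the meeting may not be the only route. Table 2 has a tolerability questionnaire given by study staff whose role is not specified, and a technician monitors every session. If the coordinator shares that work, leaving the meeting removes less of the risk. This is fair. The meeting is nevertheless a route that the protocol itself requires, and it adds regular discussion with someone who knows the arm.

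Finally, this is a pilot seeking preliminary signals, with standardized procedures and a guess at the end. Those features reduce the consequences or help to detect a problem; they do not prevent unblinding.

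**Conclusion.** The point holds as a risk of inferred or inadvertent unblinding of the outcome rater. As written, the plan has the rater attend about four per-subject reviews with the unblinded PI before mid-study testing and about eight before study-end testing, without saying how the blind is kept.

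The conclusion assumes that the coordinator attends as listed, that the individual review includes tolerability or adverse-event information, and that this information differs enough between active and sham to be suggestive. The second is the natural reading of a paragraph on safety data, and the third follows the protocol's own description of side effects; neither is stated outright.

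The reach is limited to examiner-administered Aim 2 tests in comparisons of active with sham stimulation. The Parkinson's disease aim is open label and has no blind to lose. The size of any bias is unknown. A reader might want to attach an inflated false-positive rate, but that needs an assumed shift in scores, and the documents give no basis for one. This is a cheap improvement worth making, not evidence that the results will be biased.

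**What to change.** In Section IX, Monitoring, divide the weekly meeting:

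- Individual tolerability, side-effect, clinical-course and outcome data are reviewed by the PI and those co-investigators who administer no outcome measures.
- The coordinator attends only for recruitment, scheduling and data-quality items, and gives any clinical input on a participant in writing.
- Add a sentence that the PI does not discuss arm-revealing information with the coordinator.

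The cost is a rearranged agenda, with no new staff and no change to what safety data are reviewed. The small downside is that the coordinator is absent from the per-subject discussion; written input offsets part of this.

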# IV. SPECIFIC AIMS

Specific Aim 1: To test the feasibility of a randomized, controlled remotely-supervised tDCS clinical trial protocol developed specifically for use in MS. Participants (n=85) will be randomly assigned to receive 40 x 20-minute sessions of either active (up to 2.5 mA) paired with cognitive remediation, to two separate control conditions. The first is an active tDCS condition paired with non-adaptive, traditional puzzle and board games and will act as this study's negative control. The second control will act as the study's positive control and will be sham tDCS paired with cognitive remediation. Each study session, regardless of study arm, will be followed by an additional 10 minute computerized training sessions post-stimulation. Each study arm will complete 40 sessions over eight weeks.

The *primary outcome* for feasibility will be the number of participants completing at least 80% or n=32of the targeted 40 sessions. Secondary outcomes will be comparison of tolerability and participant- reported side effects between the two treatment arms.

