
 
Able to commit to the two-week period of training sessions with baseline and follow-up visits.
 
Able to understand the informed consent process and provide consent to participate in the study
 
	
 
History of head trauma (e.g., head injury, brain surgery) in the past year or medical device implanted in the head (such as Deep Brain Stimulator) or in the neck (such as a Vagus Nerve Stimulator)
 
Any skin disorder/sensitive skin (e.g., eczema, severe rashes), blisters, open wounds, burn including sunburns, cuts or irritation, or other skin defects which compromise the integrity of the skin at or near stimulation locations (where electrodes are placed)
 
Treatment for a communicable skin disorder currently or over the past 12 months
 
History of uncontrolled or labile hypertension.
 
Other serious uncontrolled medical condition (e.g., cancer or acute myocardial infarction)
 
History of clinically significant abnormalities on electrocardiogram (EKG)
 
Alcohol or other substance use disorder
 
Learned English language after 12 years of age
 
Pregnant or breastfeeding
 
Symbol Digit Modalities Test ≥3.0 SD below published norms
 

---	---

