# **Statistical Analyses**

Analyses will be completed with IBM SPSS v. 23. Means, medians, standard deviations (SD) will be compared between subgroups on the measures using conventional cut-off points for each of the symptoms will be compared.

Specific Aim 1 will be tested by comparing the number of participants in each condition meeting the study definition of compliance (having completed 80% sessions). We will also determine the effectiveness of our sham procedures to ensure blinding, as tested by comparing those who accurately identified the sham condition. We will assess whether the frequency or type of side effects differ between the three conditions and whether they occur at the same rate as reported from studies of inclinic administration.

Specific Aim 2 will be to determine preliminary signals for efficacy, and to have pilot findings to determine necessary sample sizes for an adequately-powered clinical trial. For each participant, change scores will be calculated between baseline and study end scores on measures of fatigue and cognitive functioning. These difference scores will then be described and compared between groups (t-tests and ANOVA related analyses) to determine signals of efficacy.

Cognitive performance will be evaluated for those who completed at least 18 sessions. We conservatively plan for comparison of 15 participants in each group, allowing for up to 33% dropout. While both cognitive remediation groups are expected to improve with cognitive training, we hypothesize that the active tDCS condition will gain one standard deviation (of the published normative mean) or more in score than the sham condition and that the group with active tDCS paired with non-adaptive puzzle and board games will neither improve nor decline.

Secondary outcomes will be used to compare the groups in change in performance on the additional measures listed in Table 2. These are the most commonly-used outcome measures in MS trials

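### The hold rule's completer (5/10 sessions) and the two-week MS commitment do not fit the 40-session, eight-week MS course, and two readings of the rule can give opposite decisions

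*Combined protocol and SAP*

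**What the plan says.** All references are to the combined protocol and SAP.

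- **MS course.** Section IV, Specific Aim 1: "Each study arm will complete 40 sessions over eight weeks". Section V(a), Study Design: "Participants will complete a total of 40 sessions across eight weeks". Specific Aim 1 counts a participant as feasible at 32 of 40 sessions (80%).
- **Hold rule.** Section IX, Monitoring, puts the study on hold for review if, after the first 10 subjects, compliance in one or more arms is significantly less "relative to our previously observed compliance rates". It then sets two limbs joined by and/or. The first reads "We would define discrepancy in compliance as >50% difference in mean number of visits completed". The second is a 50% difference in the number of completers in each condition, "defined by completing at least 50% of n=5/10 sessions".
- **MS entry.** Section VII, Eligibility Criteria, MS inclusion list: "Able to commit to the two-week period of training sessions with baseline and follow-up visits".
- **Compliance elsewhere.** Section IX, Statistical Analyses, compares the arms on the number of participants "meeting the study definition of compliance (having completed 80% sessions". Section V(e) defines study success as 80% of participants completing 80% of sessions.
- **Ten-session settings.** These are the earlier open-label feasibility study (section II: n=20, 10 sessions over two weeks) and the Parkinson's aim (section XI: one open-label group, 10 days, with its own inclusion list, which also says two weeks).

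**The concern.** The completer cut-off and the MS commitment are both written for a course of 10 sessions in two weeks. The MS trial has four times that many sessions. No section rescales either rule.

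The hold rule is the only compliance check in the readable text with a stated hold threshold. If its completer limb is read at 5 sessions, almost everyone who starts treatment is a completer, and that limb says little about retention over eight weeks. If it is read as half the planned course, it asks a real question. Staff applying the rule to the same data could therefore reach different decisions. The inclusion criterion, for its part, asks for about a quarter of the commitment that the primary feasibility outcome depends on.

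The wording matches the earlier feasibility study, and the hold rule carries the citation (109) that the same section uses for that n=20 study. That it was carried over is an inference, and nothing below depends on it.

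**Working it through.** **1. The plan's own figure.** 0.50 × 10 = 5, so 5/10 reproduces on a 10-session course. On the MS course 0.50 × 40 = 20, while 5/40 = 12.5%. For the commitment, 40 sessions / 8 weeks = 5 per week, so two weeks is about 10 sessions, and 10/40 = 25%. Specific Aim 1 counts 32/40 = 80%.

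**2. Does the Parkinson's aim explain it?** No. The hold rule compares arms and conditions, and that aim has a single group. The two-week phrase also appears in the Parkinson's inclusion list, where it fits, but the MS list is separate.

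**3. Can the two readings disagree?** Let a fraction f of an arm stop at session s and the rest complete r sessions. The arm mean is m = f·s + (1 − f)·r. Let the comparator mean be M, with all comparator participants reaching session 20. The mean limb fires if (M − m)/d > 0.5. The plan does not say whether d is the larger mean, the average of the two, or the smaller.

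Take f = 1/2, s = 14, r = 40, M = 40. Then m = (14 + 40)/2 = 27 and the difference is 13:

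- larger mean: 13/40 = 32.5%
- average: 13/33.5 = 38.8%
- smaller mean: 13/27 = 48.1%

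The mean limb is silent under all three. At a 5-session cut-off, completers are 100% v 100% and the second limb is silent too. At 20 of 40 they are 50% v 100%. That meets a 50% difference exactly, in percentage points or relative to the larger share, and would not meet a limit worded as more than 50%.

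**4. How far does the illustration extend?** With M = 40 the mean limb is silent if m ≥ 20 (larger), m ≥ 24 (average) or m ≥ 26.67 (smaller). The table gives the stopping sessions s that are missed at 5 sessions but caught at 20.

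| Assumption | Larger mean | Average | Smaller mean |
|---|---|---|---|
| Half stop, rest complete 40, M = 40 | 5–19 | 8–19 | 14–19 |
| Half stop, rest complete 36, M = 40 | 5–19 | 12–19 | 18–19 |
| Half stop, rest complete 32, M = 40 | 8–19 | 16–19 | none |
| Two-thirds stop, rest complete 40, M = 40 | 10–19 | 16–19 | none |
| Half stop, rest complete 40, M = 37.6 | 5–19 | 6–19 | 11–19 |

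M = 37.6 is 94% of 40; reading the plan's compliance figure of over 94% as a share of sessions is an assumption.

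If one-third stop, completers at 20 sessions are 66.7% v 100%. The gap is 33.3 points, so rescaling does not trigger a hold. (Only division by the smaller share gives 33.3/66.7 = 50%.)

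If the comparator's completer share is 95% instead of 100%, the step 3 gap is 45 points, or 45/95 = 47.4% of the larger share. Both fall short of 50%, so even the rescaled rule would miss the example on those readings.

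**5. Cost of rescaling.** Assume a hold when any two arms differ by at least 50 points in completers, 10 participants, and no true difference between arms. Exact binomial enumeration gives these false-hold chances by the true share reaching the cut-off:

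| Arm sizes | 98% | 95% | 90% |
|---|---|---|---|
| 4/3/3 | 0.5% | 2.8% | 9.7% |
| 5/3/2 | 4.1% | 10.2% | 20.0% |
| 4/4/2 | 4.4% | 11.9% | 25.2% |

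The uneven splits are possible because randomization is stratified by SDMT and EDSS category in blocks of 3 and 6.

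**The case against.** The strongest reply is that the phrase is garbled and the 50% is what matters, with 5/10 a leftover example. On that reading the cut-off is already 20 of 40, and the step 3 arm already meets the completer limb. This stands as a limit on the consequence: any missed drop-out depends on the literal 5-session reading. It does not remove the inconsistency, because the text supports both readings and they can decide the same case differently.

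A second reply is that other safeguards exist. Weekly meetings review every subject, session counts are recorded, section VI describes checkpoints that address attendance, and consent explains the full procedures. The figure with the stop criteria is not visible, so nothing can be held against it. This also stands, and it limits what is at stake.

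A third is that with about 10 subjects at 1:1:1 an arm has three or four people, and half of three cannot occur. That is correct, and is a reason to treat step 3 as an example only.

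Three stronger readings are tempting, and the documents do not support them:

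- A reader might infer that any arm losing half its participants at sessions 14–19 passes the hold rule. Step 4 shows that this needs the rest to complete nearly all 40 sessions, a particular fraction stopping, and the 5-session reading.
- A reader might see a contradiction with section IX, Statistical Analyses: "Cognitive performance will be evaluated for those who completed at least 18 sessions". That rule selects an analysis set and need not equal a monitoring trigger. Nor does any section require the hold limit to equal the 80% success target.
- A reader might compare raw visit counts with the earlier study's 192/20 = 9.6 per person. The plan speaks of compliance rates, so that comparison is strained. It is still worth saying that visits are to be compared as shares of the planned course.

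**Conclusion.** Both mismatches are in the current text: a completer cut-off equal to 12.5% of the MS course if read literally, and an MS commitment covering about 25% of it. Confidence in these is high.

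The effect on the hold decision is conditional. Under the assumptions of step 3, the 5-session and 20-session readings give opposite decisions, the latter exactly at the boundary. The plan gives no distribution of stopping times, so how often this would occur cannot be estimated.

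The comparator is only partly specified: the trigger sentence names earlier rates, while the definition speaks of differences in each condition. The denominators are not stated.

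No analysis result is invalidated, and the Aim 1 comparison and the 80%/80% success rule are unaffected. Severity: minor.

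**What to change.** Reconcile the Monitoring paragraph of section IX and the MS inclusion list of section VII with sections IV and V(a):

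- State the MS completer as a share of the 40-session course. The rule's own 50% is 20 of 40; the threshold is for the sponsor to decide.
- Say whether the comparator is the other arms, the earlier study, or both.
- Give the denominator of each 50% difference, and say whether the completer difference is in percentage points.
- Compare visits as shares of the planned course.
- Make the MS commitment criterion cover eight weeks and 40 sessions.
- Say that the 10-session, two-week wording applies to the Parkinson's aim only. One sentence in section XI is needed, because that section otherwise adopts the section IX monitoring unchanged.

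The cost is an amendment of wording. The statistical downside is a somewhat higher false-hold chance, and only as far as fewer people reach session 20 than session 5. Step 5 puts the total for 4/3/3 arms at 0.5% if 98% truly reach the cut-off and 9.7% if 90% do, with higher figures for uneven arms.
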